## Experimental Design Schema

---

This single center/single arm, phase II clinical trial is designed to evaluate the anti-cGVHD activity of extracorporeal photopheresis (ECP) when combined with low dose IL-2, in patients with steroid refractory cGVHD, as assessed by overall cGVHD response rate (CR+PR+SD).

## Protocol Synopsis

---

Protocol Title:
A Phase II trial of extracorporeal photopheresis (ECP) plus low dose IL-2 for the treatment of steroid refractory chronic graft-versus-host disease (cGVHD)
Brief Protocol Title for the Lay Public (if applicable):
Immunotherapy with IL-2 and ECP for refractory chronic graft versus host disease
Study Phase:
Phase II, non-randomized single institution trial.
Participating Sites:
City of Hope National Medical Center
Rationale for this Study:
Impaired immune reconstitution due to alteration in the ratio of regulatory T cells (Tregs) and conventional T cells (Tcon) post hematopoietic cell transplant is responsible for clinical manifestations of chronic GVHD. We propose that the combination of ECP and IL-2 will have a synergistic effect on increasing the proportion of Tregs, leading to normalization of Treg: Tcon ratio. This should lead to improved overall response rates (CR, PR and stable disease) when IL-2 and ECP are used in combination, compared to historical controls when either modality is used alone.
Objectives:
Primary: To evaluate the anti-cGVHD activity of extracorporeal photopheresis (ECP) when combined with low dose IL-2, in patients with steroid refractory cGVHD, as assessed by overall cGVHD response rate (CR+PR+SD).
Secondary:

 
• Characterize and evaluate toxicities, including type, frequency, severity, attribution, time course and duration.
 
• Estimate overall and failure-free survival, non-relapse mortality (NRM) and relapse, through 1 year after initiation of treatment.
 
• Characterize the chronic GVHD Symptom Scale scores
 
• Determine ongoing prednisone use with IL-2 and ECP combination therapy.
 
• Assess the immunologic effects of low-dose daily SC IL-2 + ECP.
 
• Correlate clinical endpoints of response with ECP performance parameters.
 

Study Design:
Single-arm, single institution Phase II trial to estimate the activity of low dose IL-2 and ECP in patients with steroid refractory GVHD.
Endpoints:
Overall response rate to a 12-week course of subcutaneous low-dose daily IL-2 plus ECP in patients with steroid-refractory cGVHD. The primary endpoint of overall response is as defined in Section 11.0. Responses will be assessed at 3 weekly intervals while on IL-2 + ECP.
Sample Size:

The trial is expected to enroll 24 patients . Using a Simon two-stage design with type I error of 0.05 and 80% power a minimum of 24 patients are needed for enrollment to discriminate a promising response rate of 50% from current response rate of 25%

**Estimated Duration of the Study**

4years (per section 5.3)

**Summary of Subject Eligibility Criteria:**

Inclusion Criteria:

1. Recipients of allogeneic stem cell transplantation (sibling/unrelated/UCB/Haplo) with myeloablative or non-myeloablative conditioning regimens.
2. Participants must have steroid-refractory cGVHD. Steroid-refractory cGVHD is defined as having persistent signs and symptoms of cGVHD despite the use of prednisone at  $\geq$  0.20 mg/kg/day (or 0.5 mg/kg every other day) for at least 4 weeks (or equivalent dosing of alternate corticosteroids) without complete resolution of signs and symptoms. Patients with either extensive chronic GVHD or limited chronic GVHD requiring systemic therapy are eligible.
3. Patient age  $\geq$  18 years old. Because no dosing or adverse event data are currently available on the use of IL-2 in participants  $<$ 18 years of age, children are excluded from this study.
4. Estimated life expectancy greater than 3 months.
5. Karnofsky performance status of 70-100 %.
6. Stable dose of corticosteroids for 2 weeks prior to enrollment.
7. Ability to understand and the willingness to sign a written informed consent document.
8. Adequate organ function as defined below.
  - Hepatic: Adequate hepatic function (total bilirubin  $<$ 2.0 mg/dl-exception permitted in patients with Gilbert's Syndrome; AST (SGOT)/ALT (SGPT)  $\leq$ 2x ULN), unless hepatic dysfunction is a manifestation of presumed cGVHD Abnormal LFTs in the context of active cGVHD involving other organ systems may also be permitted if the treating physician documents the abnormal LFTs as being consistent with hepatic cGVHD and a liver biopsy will not be mandated in this situation.
  - Renal: Serum creatinine within normal institutional limits or creatinine clearance  $>$  60 mL/min/1.73 m^2 for participants with creatinine levels above institutional normal.
  - Adequate bone marrow function indicated by ANC $>$ 1000/mm^3 and platelets $>$ 50,000/mm^3 without growth factors or transfusions.

Exclusion Criteria:

1. Patients should not have any uncontrolled illness including ongoing or active infection. Ongoing prednisone requirement  $>$ 1 mg/kg/day (or equivalent).
2. History of thrombotic microangiopathy, hemolytic-uremic syndrome or thrombotic thrombocytopenic purpura.
3. Exposure to any new immunosuppressive medication in the 4 weeks prior to enrollment.
4. Donor lymphocyte infusion within 100 days prior to enrollment
5. Active malignant relapse.
6. Inability to comply with IL-2 treatment or ECP regimen.
7. Uncontrolled cardiac angina or symptomatic congestive heart failure (NYHA Class III or IV)
8. HIV-positive individuals on combination antiretroviral therapy are ineligible because of

the potential for pharmacokinetic interactions with the agents used after allogeneic HSCT. In addition, these individuals are at increased risk of lethal infections.

9. Patients may not be receiving any other parenteral investigational agents, or concurrent biological, chemotherapy, or radiation therapy. Oral chemotherapeutic agents or biologics –for example ruxolitinib therapy (either past or current exposure) - is allowed.
10. History of allergic reactions attributed to compounds of similar chemical or biologic composition to IL-2.
11. Patients must not have received prior chemotherapy (e.g. pentostatin) within 4 weeks before study enrollment, or those who have not recovered from the adverse events due to agents administered more than 4 weeks earlier are excluded.
12. Pregnant women are excluded from this study. Because there is an unknown but potential risk for adverse events in nursing infants secondary to treatment of the mother with IL-2, breastfeeding should be discontinued if the mother is treated with IL-2.
13. Patients with other active malignancies are ineligible for this study, other than superficial localized skin cancer (Basal or Squamous cell carcinoma).

#### **Investigational Product Dosage and Administration:**

Recombinant human IL-2 (Proleukin®) will be supplied as a sterile, lyophilized cake in single-use vials containing 22 MIU of aldesleukin intended for intravenous (IV) administration. The drug will be prepared by investigational pharmacy under aseptic conditions. The dose of  $1 \times 10^6$  IU/m^2/day for 12 weeks will be calculated based on actual body weight at screening. IL-2 will be self-administered by daily subcutaneous injection and vials will be stored at 2-8 °C. (36-46 degree F). ECP will be administered as per COH SOP. The drug will be provided by Prometheus labs and dispensed to patients by IDS pharmacy in prefilled syringes.

#### **Clinical Observations and Tests to be Performed:**

Patients will be evaluated for response to intervention (ECP + IL-2) at baseline and at weeks 3, 7, 9, 12 and 16. NIH clinical scoring forms will be used to document responses. Markers of immune activation will be monitored at the same time points from blood samples taken on scheduled clinic visits. Quality of Life Assessments will also be performed at baseline and in weeks 7 and 12.

#### **Statistical Considerations:**

The trial is expected to enroll 24 patients. Using a Simon two-stage design with type I error of 0.05 and 80% power a minimum of 24 patients are needed for enrollment to discriminate a promising response rate of 50% from current response rate of 25%

#### **Sponsor/Licensee:**

N/A

#### **Case Report Forms**

Medidata Rave EDC®

## Abbreviations

---

Abbreviation	Meaning
AE	Adverse Event
Allo-HCT	Allogeneic Hematopoietic Stem Cell Transplantation
COH	City of Hope
cGVHD	Chronic Graft-Versus-Host Disease
CR	Complete Response
CRC	Clinical Research Coordinator
CRF	Case Report Form
CTCAE	Common Terminology Criteria for Adverse Events
CTEP	Cancer Therapy Evaluation Program
DLT	Dose Limiting Toxicity
DSMC	Data Safety Monitoring Committee
ECP	Extracorporeal Photopheresis
FFS	Failure Free Survival
ICF	Informed Consent Form
IDS	Investigational Drug Services
IL-2	Interleukin-2
IND	Investigational New Drug
IRB	Institutional Review Board
MTD	Maximum Tolerated Dose
NCI	National Cancer Institute
PD	Progressive Disease
PI	Principal Investigator
PMT	Protocol Monitoring Team
PR	Partial Response
SAE	Serious Adverse Event
SC	Subcutaneous
SD	Stable Disease

## 1.0 Study Objectives

---

### 1.1 Primary Objective

To evaluate the anti-cGVHD activity of extracorporeal photopheresis (ECP) when combined with low dose IL-2, in patients with steroid refractory cGVHD, as assessed by overall cGVHD response rate (CR+PR+SD).

### 1.2 Secondary Objectives

- Characterize and evaluate toxicities, including type, frequency, severity, attribution, time course and duration.
- Estimate overall and failure-free survival, non-relapse mortality (NRM) and relapse, through 1 year after initiation of treatment.
- Characterize chronic GVHD Symptom Scale scores -self-report (with assistance from RNs and MDs).
- Determine ongoing prednisone use with IL-2 and ECP combination therapy.
- To assess efficacy of protocol therapy ( IL-2+ECP) in helping to decrease the steroid dosage.
- Assess the immunologic effects of low-dose daily SC IL-2 + ECP.
- Correlate clinical endpoints of response with ECP performance parameters.

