- B. ECP and IL-2 have non-overlapping toxicities; hence, combination of the two should be well tolerated in patients with cGVHD. This combination is already being used off protocol (n=7) at COH after case review and approval by the GVHD committee in patients with cGVHD and the combination is well tolerated in patients treated so far. Patients on this combination have not experienced disease progression and all have derived clinic benefit from disease stabilization or partial responses.
- C. Relapse of cGVHD is frequently noted after discontinuation of IL-2 therapy, possibly related to decline in Tregs to baseline after stopping low dose IL-2 therapy. After completion of protocol specified therapy at 12 weeks, responding patients will continue daily low dose subcutaneous IL-2 (commercial supply) and ECP (per SOP) till clinical benefit is no longer maintained. The decision to continue commercial supply of IL-2 will be per discretion of the treating primary physician in consultation with specialists in cGVHD clinic. No protocol specific monitoring or follow up data will be collected. Monitoring of these patients will be according to acceptable standard of care for patients on cytokine therapy. Ongoing responses will be monitored by the NIH consensus criteria guidelines, again off protocol. We hypothesize that maintenance therapy with IL-2 and ECP will maintain elevated T reg: Tcon ratio, thereby translating into fewer clinical relapses and improved clinical outcomes.

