#### 5.2 Treatment Schedule

##### 5.2.1 IL-2 Therapy

D. IL-2 will be self-administered by patients as a daily subcutaneous injection. Teaching will be provided before the first subcutaneous injection. The pharmacist, or the primary pharmacy technician working under the supervision of the pharmacist, will prepare the drug under aseptic conditions. The amount (in IU) of drug to be administered will be determined based on body surface area (BSA). The dose should be calculated based on body weight at screening, at a dose of  $1 \times 10^6$  IU/m^2/day for 12 weeks. All treatments will be outpatient based. If however, patients live within a 15 mile distance of the medical center and /or insurance mandates that the IL-2 be given in physician office- IL-2 injections will be given in the infusion center. After completion of 12 weeks of protocol therapy, responding patients will have the option of continuation of therapy till clinical benefit is no longer maintained. IL-2 will be provided by Prometheus Labs for this study. No protocol specific monitoring or follow up data will be collected after initial 12 week period. Monitoring of these patients will be according to acceptable standards of care for patients on cytokine therapy with IL-2. Ongoing responses will be monitored by the NIH consensus criteria guidelines , again off protocol . We hypothesize that maintenance therapy with IL-2 and ECP will

maintain elevated T reg: Tcon ratio, thereby translating into fewer clinical relapses and improved clinical outcomes.

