### **5.3 Planned Duration of Therapy:**

IL-2 and ECP combination therapy will be given for 12 weeks, with final immune assessment occurring at 16 weeks post-initiation of therapy. Patients deemed to be benefiting from combination therapy (i.e. in complete remission, partial remission, minor response or stable disease), will have the options to continue onto the extended duration per discretion of treating physician.

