### **5.4 Optional Extended-duration therapy:**

As mentioned in the section above, patients who are responding to upfront therapy with IL-2 and ECP will be eligible to continue combination therapy with daily subQ IL-2 and ECP per SOP guidelines till clinical benefit is no longer maintained or toxicities develop. While on the optional maintenance therapy, these patients will be monitored for response and toxicity profile in the GVHD clinic on a monthly basis. This monitoring will not require data collection from research staff for response or adverse effect monitoring. Best clinical judgment will be used to determine on each monthly visit on rationale to continue commercial supply IL-2 or not based on clinical benefit and adverse effect profile of IL-2.

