### **5.5 Criteria for Removal from Treatment**

- Subject withdraws consent
- Non-compliance
- Administrative reasons (insurance loss or no coverage of IL-2 or ECP by third party payors)
- Any Grade 4 non hematologic adverse event
- Life threatening anaphylactic reaction to IL-2
- Recurrent or non-resolving grade 3 toxic event
- Malignant relapse
- Clinical worsening of GVHD requiring the addition of a new immunosuppressive medication. A 50% increase in the corticosteroid dose will be considered evidence of worsening GVHD. Changes in other immunosuppressive medication doses to maintain a therapeutic level alone will not be criteria for removal from the trial.

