### **5.6 Subject Follow-Up**

While on the first twelve weeks of therapy, participants will be undergo clinical (including cGVHD) and immunologic evaluations every 3 weeks. cGVHD severity/response will be assessed using the NIH scoring criteria (see Appendix).

Toxicity assessments will be performed using the CTEP Version 4.03 of the NCI Common Terminology Criteria for Adverse Events (CTCAE) which is identified and located on the CTEP website at: [http://ctep.cancer.gov/protocolDevelopment/electronic\\_applications/ctc.htm](http://ctep.cancer.gov/protocolDevelopment/electronic_applications/ctc.htm).

If possible, adverse effects should be managed symptomatically. In the case of toxicity, appropriate medical treatment should be used (including anti-emetics, anti-diarrheals, etc.). All CTCAE grade 3 and higher adverse events experienced by participants will be collected from the time of the first dose of study treatment, through the study and until the final study visit.

Participants removed from the study for unacceptable adverse events will be followed until resolution or stabilization of the adverse event. Follow-up for participants benefiting on extended-duration therapy will continue on monthly basis in the GVHD clinic.

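### OS, FFS, NRM and relapse are promised through 1 year, but no visit or call after week 16 is defined to collect them

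*Combined protocol and SAP*

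**What the plan says.** The Synopsis and section 1.2 carry the same secondary objective: "Estimate overall and failure-free survival, non-relapse mortality (NRM) and relapse, through 1 year after initiation of treatment". Section 11.2 measures OS, FFS and NRM from the first dose. FFS ends at documented cGVHD progression that forces a treatment change, at malignancy relapse or progression, or at death. NRM counts deaths in patients whose malignancy is not active, so it needs disease status at death.

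The schedule stops much earlier. Section 5.3 has the "final immune assessment occurring at 16 weeks post-initiation of therapy". The calendar in section 10.0 has no column after week 16. In section 11.2, steroid dose and immune assessment end at week 16, or 4 weeks after treatment ends. Section 7 records adverse events, deaths included, up to 30 days after the last IL-2 injection.

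For responders who continue therapy, section 5.2.1 says: "No protocol specific monitoring or follow up data will be collected after initial 12 week period". Section 2.1.4 says of the same patients: "No protocol specific monitoring or follow up data will be collected". Section 5.4 sends them to a monthly clinic and adds: "This monitoring will not require data collection from research staff for response or adverse effect monitoring".

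Section 5.6 has two provisions that can run later: "Participants removed from the study for unacceptable adverse events will be followed until resolution or stabilization of the adverse event", and "Follow-up for participants benefiting on extended-duration therapy will continue on monthly basis in the GVHD clinic". The reasons for removal in section 5.5 include malignant relapse and "Clinical worsening of GVHD requiring the addition of a new immunosuppressive medication".

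Section 12.1.3 lists a Follow up/Survival Form. Its due date is counted from a visit or call that the protocol is supposed to define. The available text defines none.

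**The concern.** An objective with a 1-year horizon needs a stated way of learning, for every treated patient, whether and when an event occurred in that year. Here the horizon is month 12 and the schedule ends at about month 4. For continuing responders the text goes further and says that protocol follow-up data are not collected.

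Without set contacts, capture of events depends on who stays in clinic. There are three ways this could go:

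- If every survivor is censored near week 16, nobody is at risk at month 12 and Kaplan-Meier gives no 1-year estimate.
- If only clinic attenders are followed, the 1-year estimates rest mainly on patients selected for benefit.
- If patients with unknown status are counted as event-free, each missed event makes the result look better than it was.

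Section 13.2 names Kaplan-Meier for survival but gives no censoring rule that would settle which of these applies.

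**Working it through.** **The plan's own figures.** Section 13.1 expects 24 patients at 6 per year: 24/6 = 4 years of accrual. The Synopsis gives an estimated study duration of 4 years and cites section 5.3. That section gives only 12 weeks of therapy and a week-16 assessment. The stated duration therefore equals the accrual period alone. The two-stage design also reproduces (stop at 2 or fewer of 9, reject at 10 or more of 24: exact type I error 0.0485, power 0.805). No sample-size or precision figure is given for the 1-year endpoints.

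**Gap by patient group**, against a 52-week horizon:

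| Patient | Last scheduled protocol assessment | Gap to week 52 |
|---|---|---|
| Stops at week 12 | Week 16 | 52 − 16 = 36 weeks (69%) |
| Responder who continues, under 5.2.1 | Week 12 | 52 − 12 = 40 weeks (77%) |
| Stops early, for example at week 4 | 4 + 4 = week 8 | 52 − 8 = 44 weeks (85%) |

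The adverse-event window does not close the gap: 12 weeks is 84 days, and 84 + 30 = 114 days, or week 16.3.

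**What remains open after removal from treatment:**

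- Removed for malignant relapse: the FFS and relapse events have already occurred. Mainly OS remains.
- Removed for worsening GVHD that needs a new drug: the FFS event has largely occurred. It is not certain in every case, because section 11.1.1 separates clinical worsening from progression by NIH criteria. OS, NRM and relapse remain open.
- Removed for an adverse event: followed until that event resolves or stabilizes, which is not a fixed follow-up for the four endpoints.

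**Size of one missed event** if it is counted as event-free: 1/24 = 4.2 points. If the trial stops after stage 1: 1/9 = 11.1 points.

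**How much of the first year lies in the gap (illustration).** Section 2.1.1 cites a 6-month FFS of 56% for second-line therapy. Assume a constant hazard and similar patients. FFS at week 16 is then 0.56^(16/26) = 0.70, and at 1 year 0.56² = 0.31. The share of first-year failures after week 16 is (0.700 − 0.314)/(1 − 0.314) = 56%. The share runs from 49% to 61% if the 6-month FFS is 40% to 70%.

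**Duration.** Following the last patient for 1 year needs 4 + 1 = 5 years. If data closed at 4 years with uniform accrual, the last year's 6 × 1 = 6 entrants would be short of 1 year. At an assumed 70% survival, the 1-year standard error with full follow-up is √(0.7 × 0.3/24) = 9.4 points. The large-sample Kaplan-Meier variance under exponential survival, with entry uniform over 4 years, gives 10.1 points. The increase is 7–8% for survival from 50% to 90%.

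**The case against.** Follow-up was clearly planned. A Follow up/Survival Form exists, continuing patients are seen monthly, and this is a single centre where dates of death and relapse can be taken from charts. The no-data sentences in 2.1.4 and 5.2.1 stand in text about responders who continue, and 5.4 waives only response and adverse-effect data. Nothing waives survival or relapse data for patients off IL-2. All of this stands. A reader might infer that the plan abandons the 1-year commitment, or bars follow-up for everyone. The documents do not support that. What they show is a form without a defined date, and a statement about one subgroup that conflicts with the objective.

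A reader might also infer that patients off therapy have no further contact at all. Section 11.2 does provide assessments 4 weeks after end of treatment. The gap starts after that.

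It may also be tempting to read the 4-year duration as a source of bias. It is only an estimated duration, and no passage stops data collection then. Even if one did, administrative censoring of late entrants would cost modest precision and would not by itself bias the estimates.

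The conflict with the week-16 assessments is partly ambiguous. Section 9.1 describes the last sample as 4 weeks after stopping, which is week 16 for those who complete treatment. Section 5.3 and the calendar show week 16 without that condition.

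The objection does not supply the missing piece. Monthly clinic visits are off protocol and cover only patients who benefit. Adverse-event follow-up ends with the event. If chart review is the intended source, the plan does not say so.

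**Conclusion.** The conflict is real and should be fixed. Four secondary endpoints are promised through 1 year, and as written 36 to 40 of the 52 weeks have no scheduled protocol data for patients who complete 12 weeks. The gap is longer for early stoppers. The possible error is 4.2 points per missed event at 24 patients and 11.1 points at 9. Both figures assume that missed events are counted as event-free, and that nobody else is censored.

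The primary endpoint, the sample size and the stopping rules are unaffected. The loss also differs by group: relapse removals lose mainly OS, and removals for worsening GVHD lose OS, NRM and relapse more than FFS. Section 13.2 names no method for NRM or relapse, but that is a separate missing detail and not part of this conflict.

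The conclusion rests on the available text. The treatment schema in section 5.1 survives only in part and the appendices are not included. If either defines the follow-up contacts, what remains is to reconcile them with 2.1.4, 5.2.1 and 5.4.

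**What to change.** Add to section 5.6 and the calendar wording such as:

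> For every treated patient, on or off IL-2, the following are recorded at months 6 and 12 after first dose, by chart review or call, on the Follow up/Survival Form: vital status; malignancy relapse, with disease status at death; and the date of and reason for any change in systemic cGVHD therapy, including whether cGVHD progression as used in the FFS definition was documented.

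Then:

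- Name these in section 12.1.3 as the contacts that trigger the form.
- Exempt these items from the no-data statements in 2.1.4, 5.2.1 and 5.4.
- Reconcile the week-12 cut-off in 5.2.1 with the week-16 assessments.
- State the study duration as about 5 years (4 years of accrual plus 1) and correct its cross-reference to 5.3.

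If 1-year follow-up is not wanted, restate the objectives to a shorter horizon and collect vital status, relapse and therapy change to that horizon for all treated patients. Changing the horizon to week 16 would not be enough alone: a patient who stops at week 4 is last assessed at week 8 and would still have 16 − 8 = 8 weeks uncovered.

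The cost is amendment wording, at most 24 × 2 = 48 chart reviews or calls, and about one more year before the final secondary results. No extra procedure is needed, and the primary analysis need not wait.
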